3. OBJECTIVES AND ENDPOINTS

Table 3 Study objectives and endpoints

[figure not shown]
Objectives	Endpoints
	Primary
Co-primary Immunogenicity: • To evaluate whether the monovalent influenza A/Hong Kong/125/2017-like (H7N9) virus vaccine containing 1.9 µg, 3.75 µg, or 7.5 µg of hemagglutinin (HA) adjuvanted with AS03 _A or AS03 _B elicits a hemagglutination inhibition (HI) antibody response to the vaccine-homologous virus that meets or exceeds the US Food and Drug Administration, Center for Biologics Evaluation and Research immunogenicity criteria at the Day 43 visit.	
 • Humoral immune response in terms of vaccine-homologous HI antibody titers: 
 – Seroprotection rates (SPR) at Day 43 – Seroconversion rates (SCR) at Day 43
Safety: • To describe the safety and reactogenicity of the different vaccine formulations through the Day 43 visit.	
 • Occurrence of adverse events (AEs) 
 – Solicited administration site events during a 7-day follow-up period (i.e. day of vaccination and 6 subsequent days) after each vaccination – Solicited systemic events during a 7-day follow-up (i.e. day of vaccination and 6 subsequent days) after each vaccination – Unsolicited AEs and medically attended adverse events (MAEs) for 21 days after each vaccination – Serious adverse events (SAEs), potential immune-mediated disease (pIMDs) up to Day 43 visit
Safety: • To describe the safety of the different vaccine formulations through Month 13	
 • Occurrence of pIMDs and SAEs until Month 13
	Secondary
• To describe the vaccine homologous H7N9 HI antibody profile in all study groups at Days 1, 22, and 43	
 • Vaccine-homologous (H7N9) HI antibody titers for each study group: 
 – Geometric Mean Titers (GMTs) at Days 1, 22, and 43 – Seropositivity rates at Days 1, 22 and 43 – SCR at Days 22 – SPR at Days 1 and 22 – Mean Geometric Increase (MGI) at Days 22 and 43
• To describe the vaccine homologous (H7N9) Microneutralization (MN) antibody profiles in a subset of participants at Days 1, 22, and 43	
 • Vaccine-homologous (H7N9) MN antibody titers for subset of participants: 
 – GMTs at Days 1, 22, and 43 – Seropositivity rates at Days 1, 22, and 43 – Vaccine response rate (VRR) at Days 22 and 43

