9.4.3.2. Safety

The analysis of reactogenicity and unsolicited events will be based on the ES.

Solicited administration site and systemic endpoints

- Occurrence of each solicited administration site events during a 7-day follow-up period (Day 1 to Day 7) after each vaccination.
- Occurrence of each solicited systemic events during a 7-day follow-up period (Day 1 to Day 7) after each vaccination.

All solicited events will be summarized according to defined severity grading scales.

Frequencies and percentages of participants experiencing each event will be presented for each symptom severity. Summary tables showing the occurrence of any solicited administration site events or solicited systemic events overall and at each time point will

also be presented and will be tabulated with Clopper-Pearson exact 95% CIs. Solicited administration site events will be assessed according to which vaccine was administered.

If a solicited event occurs more than once for a participant, it will be counted in the summary only once for each level of summarization, according to the maximal severity. Summary tables showing the occurrence of any solicited administration site events or solicited systemic events overall will be presented.

Unsolicited AE endpoints (Amended 22 February 2022)

- Occurrence and relationship to vaccination of unsolicited AEs within 21 days after each vaccination.
- Occurrence and relationship to vaccination of AEs with MAEs within 21 days after each vaccination.

SAE endpoints

- Occurrence and relationship to vaccination of SAEs and pIMDs up to Day 43 visit.
- Occurrence and relationship to vaccination of SAEs and pIMDs until Month 13.

This analysis applies to all AEs, whether judged either as probably related, possibly related, or not related to vaccination by the investigator, recorded in the Adverse Events eCRF, with a start date on or after the date of first vaccination and not later than 21 days of the most recent vaccination. Adverse events starting prior to the first vaccination will only be listed. The original verbatim terms used by investigators to identify AEs in the eCRFs will be mapped to preferred terms using the Medical Dictionary for Regulatory Activities. The AEs will then be grouped by Medical Dictionary for Regulatory Activities preferred terms into frequency tables according to system organ class.

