The following administration site events will be solicited:

Table 17 Solicited administration site events

All age groups
Pain
Redness
Swelling

b. **Solicited systemic events**

The following systemic events will be solicited:

Table 18 Solicited systemic events

All age groups
Fatigue
Fever
Headache
Muscle ache all over body
Joint pain
Shivering (Chills)
Sweating
Gastrointestinal symptoms:
Nausea
Vomiting
Diarrhea
Abdominal pain

Note: participants will be instructed to measure and record the oral body temperature in the evening. Should additional temperature measurements be performed at other times of day, participants will be instructed to record the highest temperature in the diary card.

10.3.4. **Unsolicited adverse events**

An unsolicited AE is an AE that was not solicited using a Participant Diary and that was spontaneously communicated by a participant who has signed the informed consent.

Unsolicited AEs include serious and non-serious AEs.

Potential unsolicited AEs may be medically attended (i.e., symptoms or illnesses requiring a hospitalization, or emergency room visit, or visit to/by a health care provider). The participants will be instructed to contact the site as soon as possible to report MAE(s), as well as any events that, though not medically attended, are of participant concern. Detailed information about reported unsolicited AEs will be collected by qualified site personnel and documented in the participant's records.

Unsolicited AEs that are not medically attended nor perceived as a concern by participant will be collected during interview with the participants and by review of available medical records at the next visit.

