10.3.9.3. Medically attended visits

For each solicited and unsolicited symptom the participant experiences, the participant will be asked if he/she received medical attention defined as hospitalization, or an otherwise unscheduled visit to or from medical personnel for any reason, including emergency room visits. This information will be recorded in the eCRF.

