In order to minimize the effect of missing data, the study period will be divided into time intervals for the safety analyses. For unsolicited AEs, the study period will be divided into the following intervals: all unsolicited AEs and MAEs reported from Day 1 to Day 21 after each vaccination, AEs leading to premature withdrawal from the study during the entire study period, SAEs reported during the entire study period and pIMD reported during the study period for the Exposed Set. Unsolicited AEs will be assigned to the study periods based upon the start date and times recorded in the eCRF. Concomitant medications will be assessed up to 21 days after each vaccination for the Exposed Set in a summary table. All concomitant medications collected in the database will be presented in a data listing.

A participant will be classified as having missing data within the specified intervals as described below:

Category	Regarded as Missing When:
Non serious AEs	No AEs are recorded and there is no response to “Have any non-serious adverse events occurred which are required to be reported as per protocol?” (Non Serious Adverse Event YN electronic Case Report Form [eCRF] page).
Medically attended AEs	If AEs are recorded and there is no response to “Medically attended visit” (Non Serious Adverse Events eCRF page or Serious/Expedited Event eCRF page).
AEs leading to withdrawal from the study vaccine	If AEs are recorded and there is no response to “Action Taken with study vaccine(s) as a Result of the AE” (Non Serious Adverse Events eCRF page or Serious/Expedited Event eCRF page).

Serious AEs	If no SAEs are recorded and there is no response to “Did the subject experience any Serious Adverse Event and/or pIMD and/or other AESI and/or Non-Serious related AE (ADR) that are required to be reported per protocol?” (Serious/Expedited Event YN eCRF page), or if the answer was “Yes” and there is no response to “Serious?” (Serious/Expedited Event eCRF page).
pIMD	No pIMD events recorded and there is no response to “Did the subject experience any Serious Adverse Event and/or pIMD and/or other AESI and/or Non-Serious related AE (ADR) that are required to be reported per protocol?” (Serious/Expedited Event YN eCRF page), or if the answer was “Yes” and there is no response to “Adverse Event of Special Interest (AESI)?” (Serious/Expedited Event eCRF page).

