9.1 Adverse Events

Solicited events, unsolicited AEs, SAEs, medically attended AEs, AEs leading to withdrawal from intervention or from the study, and pIMDs that occur post-vaccination will be summarized and also presented in listings. AEs occurring prior to a participant receiving any study vaccine will be listed only.

The definitions for SAEs and medically attended AEs can be found in protocol sections 10.3.2 and 10.3.9.3 respectively. Further information about pIMDs can be found in protocol section 10.3.5.1.

Incomplete onset dates and end dates for any AEs will be imputed to determine if the event occurred within the time period specified for AE summaries that are described in sections 0 and 9.1.2. Actual dates recorded will be presented in listings, imputed dates will not be presented. Incomplete dates will be imputed as follows:

Missing onset dates (where UK and UKN indicate unknown or missing day and month respectively):

- If the response to “If exact start date is unknown, or is on the same day as any study vaccination, please confirm whether it occurred before or after vaccination:” is “After vaccination 1” or “After vaccination 2” then assume the start date is the date of the first and second dose of study vaccine, respectively.
- If the response is “Before vaccination” assume the following:
 - UK-MMM-YYYY: If the month and year are different from the month and year of the first dose of study vaccine, assume 01-MMM-YYYY. If the month and year are the same as the first dose of study vaccine month and year, and the end date (after any imputation) is on or after the first dose of study vaccine, then assume the date of the first dose of study vaccine. If the month and year are the same as the first dose of study vaccine month, and year and the end date (after any imputation) is prior to the first dose of study vaccine, then assume the end date for the onset date.

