9.1.2 Unsolicited Adverse Events

An unsolicited AE is an AE that was not solicited using a participant Diary and that was spontaneously communicated by the participants or a solicited administration site or systemic event that meets the criteria described in Section 0. Solicited events lasting more than 7 days after vaccination (including the day of vaccination) are also recorded as unsolicited AEs.

The original verbatim terms used by investigators to identify AEs in the Adverse Events page of the eCRF will be mapped to preferred terms (PT) using MedDRA, version to be delineated in the CSR. The AEs will then be grouped by MedDRA according to system organ class (SOC).

The following summaries will present the event count, number and percentage of participants reporting each AE and will be presented by SOC, PT, and maximum relationship to study intervention for each study group, grouped by 21 days post-vaccination at any visit and then by 2 time points (at the final analysis): 21 days post-vaccination at Visit 1, and 21 days post-vaccination at Visit 2:

- Any unsolicited AE
- Any severe unsolicited AE (grade 3)
- Any related unsolicited AE
- Any severe related unsolicited AE (grade 3 related)
- Unsolicited MAEs
- Any AEs with MAEs
- Any related AEs with MAEs

Additional summaries will present the number and percentage of participants reporting AEs in the following categories and will be presented by SOC and PT for each study group and age group from Day 1 through the Day 43 visit and from Day 1 through the end of study:

- SAEs
- AEs leading to withdrawal from study drug (through Day 22 only)
- AEs leading to withdrawal from study
- MAEs (within 21 days post each vaccination)
- pIMDs

Data listings of all AEs will be provided by participant. In addition, AEs in the categories above will be provided as listed data.

Missing data will be handled as described in Section 4.5.

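### The plan gives no path into any MAE summary for a non-serious, medically attended solicited reaction that starts and resolves within Days 1-7, although the SAP's own MAE definition covers it.

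*SAP*

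**What the plan says.** **Endpoint.** Protocol Section 3 (Table 3) lists among the primary safety endpoints "Unsolicited AEs and medically attended adverse events (MAEs) for 21 days after each vaccination". SAP 3.2.1 repeats this.

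**Definition.** SAP 9.1 states: "The definitions for SAEs and medically attended AEs can be found in protocol sections 10.3.2 and 10.3.9.3 respectively". Protocol 10.3.9.3 reads: "For each solicited and unsolicited symptom the participant experiences, the participant will be asked if he/she received medical attention defined as hospitalization". It goes on to include other unscheduled contacts with medical personnel, emergency room visits among them, and says that the answer goes into the eCRF. It does not name the page.

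**Analysis.** Protocol 9.4.3.2 applies the AE analysis to events "recorded in the Adverse Events eCRF, with a start date on or after the date of first vaccination". SAP 9.1.2 presents its MAE summaries by system organ class and preferred term, and says that investigators' terms used "to identify AEs in the Adverse Events page of the eCRF will be mapped to preferred terms". SAP 4.5, in its missing-data rule for MAEs, locates the medically attended item on the "Non Serious Adverse Events eCRF page or Serious/Expedited Event eCRF page". Solicited events have two eCRF pages of their own. SAP 4.5 describes these by leading questions, intensities and measurements. SAP 9.1.1 summarises solicited events by occurrence, maximal severity and duration.

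**The concern.** The definition and the tabulation do not cover the same events. By the SAP's own reference, a solicited reaction for which the participant sought care is an MAE. The tables that report MAEs are built from records where such a reaction appears only under certain conditions.

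Protocol 10.3.9.2 treats every solicited event as causally related to vaccination. Any event missed in this way would therefore be a related one, and the row in SAP 9.1.2 for related AEs with MAEs would be affected as well as the overall count. Two programmers working from the present text could also produce different tables for a primary safety endpoint.

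**Working it through.** The plan states no MAE rate, so there is no figure to reproduce. The check follows a medically attended solicited reaction through the text.

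| Type of medically attended solicited reaction | Route into an MAE summary | Source |
|---|---|---|
| Serious (hospitalization makes it so) | Yes: Serious/Expedited page, which carries the medically attended item | Protocol 10.3.2; SAP 4.5 |
| Continues past Day 7 | Yes: recorded as an unsolicited AE | Protocol 10.3.8; SAP 9.1.2 |
| Starts after Day 7 | Yes: recorded as an unsolicited AE | Protocol 10.3.8 |
| Non-serious, starts and resolves within Days 1-7 | None stated | Protocol 9.4.3.2; SAP 4.5, 9.1.1, 9.1.2 |

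Two passages might open a route for the last row.

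1. *The reference to Section 0.* SAP 9.1.2 counts as unsolicited any solicited event that meets criteria in a Section 0, which does not exist. SAP 9.1 pairs the same broken number with 9.1.2 when it speaks of the AE summaries, so 9.1.1 is the likeliest target. SAP 9.1.1 contains no medical-attention criterion. On that reading nothing is admitted; on any other, the rule cannot be read.
2. *The row labels.* SAP 9.1.2 lists *Any AEs with MAEs* and a plain *MAEs* row apart from *Unsolicited MAEs*. The difference is not defined. If solicited events are meant, the SAP names no source field, coding step or missing-data rule for them.

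Neither gives a route that could be programmed from the text.

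**Size.** The documents give no rate for this class of event, so the figures below rest on an assumed share r of vaccinees with such a reaction and no other MAE.

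- Effect of one participant: 1/60 = 1.7 percentage points in an age-by-group cell, and 1/120 = 0.8 points in a study group.
- Chance that a cell of 60 misses at least one: 1 − (1 − r)^60.
- Expected number missed among the 6 × 120 = 720 vaccinees: 720r.

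| Assumed r | Chance a cell of 60 misses at least one | Expected number missed of 720 |
|---|---|---|
| 0.5% | 26% | 3.6 |
| 1% | 45% | 7.2 |
| 2% | 70% | 14.4 |
| 5% | 95% | 36 |

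**The case against.** The strongest reply is that the SAP follows the protocol's endpoint. Protocol 9.4.3.2 lists AEs with MAEs under its unsolicited AE endpoints. Protocol 10.3.4, on unsolicited events, says "Potential unsolicited AEs may be medically attended". Table 3 and the schedule of activities pair MAEs with unsolicited AEs. Protocol 10.3.9.3 is headed as being about visits, and it says that a question is asked, not that each positive answer counts towards the endpoint. On this view MAEs were always meant to be unsolicited.

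Part of this stands. It would be too strong to say that the protocol itself counts these reactions as MAEs; that follows only through the SAP's cross-reference. But SAP 9.1 chose 10.3.9.3 as the definition, and 10.3.4 does not say that only unsolicited events qualify. The conflict is real and needs a decision.

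A reader might also infer that medically attended solicited reactions never reach an MAE table, or that the SAP expressly confines the MAE analysis to the AE pages. The documents do not support either. Three of the four types in the table above do arrive. The sentence quoted from 9.1.2 concerns MedDRA coding, and the one from 4.5 is a missing-data rule. They show where the plan expects the data to be, not a stated exclusion.

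Nor do the documents show that the vaccine-placebo contrast is understated. More such events in the vaccine arms is plausible, but no rates are given. SAP 4.2 makes the safety analyses descriptive, without p-values, so no formal comparison is affected. The reactions themselves are still tabulated by severity and listed; it is their medical-attention status that may go unsummarised.

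Finally, merging diary events into coded system-organ-class tables is open to dispute. That objection is fair, and the fix below avoids it.

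**Conclusion.** The point holds for one class of event: non-serious, medically attended solicited reactions that start and resolve within Days 1-7 of a dose. They meet the definition that SAP 9.1 adopts, and the plan gives them no path into an MAE summary. Followed as written, the MAE part of the primary safety endpoint undercounts relative to that definition.

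The size of the undercount is unknown; the range shown rests wholly on assumed rates. The conclusion assumes that SAP 9.1 means its cross-reference to Protocol 10.3.9.3, and that the eCRF and table shells, which are not among the documents, supply no route that the text omits. This should be corrected in the SAP. It does not touch the immunogenicity hypotheses or the conduct of the trial.

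**What to change.** - **SAP 9.1.1:** add the number and percentage of participants with a medically attended solicited event, by dose, study group and age group.
- **SAP 9.1.2:** define *Any AEs with MAEs* as the participant-level count of any medically attended event, solicited or unsolicited, within 21 days of a dose. Keep *Unsolicited MAEs* as the table by system organ class and preferred term, and state which definition the remaining MAE rows use.
- **SAP 9.1 and 9.1.2:** repair the references to Section 0.
- **SAP 4.5:** name the eCRF field that holds the medical-attention answer for solicited symptoms required by Protocol 10.3.9.3, and extend the MAE missing-data rule to it.

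The cost is SAP wording and programming, and the reported MAE rate may rise slightly. Protocol 10.3.9.3 says that the answers are recorded, so no new collection should be needed; the sponsor should confirm this when naming the field.

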3.2 Study Endpoints

3.2.1 Primary Endpoints

Immunogenicity Endpoints

- Humoral immune response in terms of vaccine-homologous HI antibody titers:
 - Seroprotection rate (SPR) at Day 43
 - Seroconversion rate (SCR) at Day 43

Safety Endpoints

- Occurrence of AEs
 - Solicited administration site events during a 7-day follow-up period (i.e. day of vaccination and 6 subsequent days) after each vaccination
 - Solicited systemic events during a 7-day follow-up (i.e. day of vaccination and 6 subsequent days) after each vaccination
 - Unsolicited AEs and MAEs for 21 days after each vaccination
 - SAEs, pIMDs up to Day 43 visit
 - pIMDs and SAEs until Month 13

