- Blinded listing of pregnancies and withdrawals due to AEs collected up to the Day 43 post-vaccination visit will be presented.
- Results will be presented in a Day 43 statistical report. Access to individual intervention codes will be restricted to the designated unblinded statisticians in charge of the analysis. No individual listings or data with the participants' identifying information will be disseminated. Listings of final data will be provided with the Month 13 report.

All analyses will be performed on data that has been cleaned and locked. The possibility of post-analysis changes to data evaluated at Day 43 exists, since data

collection and data entry may continue through Month 13. All final data will be presented in the listings provided at Month 13.

10.3 Final Analysis at Month 13

A final data analysis will be performed at the end of study (Month 13) of all primary and secondary endpoints based on the clean data, including evaluations of:

- Immunogenicity at all measured time points (Days 1, 22 and 43).
- Solicited administration site events and solicited systemic events data reported 7 days after each vaccination (Day 1 to Day 7 and Day 22 to Day 28).
- Unsolicited AEs and MAEs reported up to 21 days after each vaccination.
- Concomitant medications reported up to 21 days after each vaccination.
- SAEs, pIMDs and withdrawals due to AEs collected throughout the entire study.
- Pregnancies throughout the entire study.

An integrated CSR containing all data will be written and made available to the investigators.

10.4 Statistical Considerations for the Analysis at Day 43

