Since the primary immunogenicity endpoints for the study will be complete by the Day 43 visit (collection past Day 43 includes only assessments for unsolicited AEs leading to study withdrawal, SAEs and pIMDs), no statistical consideration for multiplicity will be given to account for changes in the results reported at the interim analysis compared to the final analysis. For the primary immunogenicity analysis, which will be reported at Day 43 the overall type I error rate is fixed at 5% (two-sided intervals) and a Bonferroni adjustment will be applied to allow simultaneous multiple comparisons of each antigen/adjuvant group. No further adjustment is needed since sequential testing will be used for each antigen/adjuvant group related to the two endpoints and to the two age categories. For the secondary immunogenicity and primary safety analyses no adjustment for multiple comparisons will be made in each antigen/adjuvant group as the CIs are provided for descriptive purposes only. No adjustment is applied for the Placebo group.

11 Changes to the Protocol Planned Analysis

The duration of solicited events will also be summarized by study group, age group and vaccination.

12 References

Center for Biologics Evaluation and Research (CBER). Guidance for Industry. Clinical data needed to support the licensure of pandemic influenza vaccines. May 2007. <https://www.fda.gov/regulatory-information/search-fda-guidance-documents/clinical-data-needed-support-licensure-pandemic-influenza-vaccines>.

Food and Agriculture Organization of the United Nations (FAO). Agriculture and Consumer Protection Department. Animal Production and Health. H7N9 situation update. Avian Influenza A (H7N9) 4 September 2019. http://www.fao.org/ag/againfo/programmes/en/empres/h7n9/situation_update.htm. Accessed 2 October 2019.

World Health Organization (WHO). Avian Influenza Weekly Update Number 694. 20 September 2019. https://www.who.int/docs/default-source/wpro---documents/emergency/surveillance/avian-influenza/ai-20190920.pdf?sfvrsn=30d65594_36. Accessed: 2 October 2019

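### SAP 9.1.2 tabulates SAEs and pIMDs to Day 43 and Month 13 without relationship to vaccination, which Protocol 9.4.3.2 includes in two primary safety endpoints

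*SAP*

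**What the plan says.** The endpoint is worded in two ways.

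- Protocol 9.4.3.2, under primary endpoints, gives "Occurrence and relationship to vaccination of SAEs and pIMDs up to Day 43 visit" and "Occurrence and relationship to vaccination of SAEs and pIMDs until Month 13".
- Protocol Table 3 gives the Month 13 endpoint as "Occurrence of pIMDs and SAEs until Month 13". SAP 3.2.1 follows Table 3: under the occurrence of AEs it lists "pIMDs and SAEs until Month 13". Neither mentions relationship.

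SAP 9.1.2 then plans two blocks of tables.

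- The first is by SOC, PT and "maximum relationship to study intervention for each study group, grouped by 21 days post-vaccination at any visit", with a split by dose at the final analysis. It covers unsolicited and medically attended AEs and has rows for related events. SAEs and pIMDs are not among its categories.
- The second contains the SAE and pIMD tables. These "will be presented by SOC and PT for each study group and age group from Day 1 through the Day 43 visit and from Day" (this second period ends with the study). Relationship is not a dimension of this block.

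SAP 9.1.2 also plans participant listings of all AEs, with SAEs and pIMDs listed as categories of their own. For the Day 43 report, SAP 10.2 states: "No individual listings or data with the participants' identifying information will be disseminated". Final listings come with the Month 13 report. SAP 11 declares one change from the protocol's planned analysis: "The duration of solicited events will also be summarized by study group, age group and vaccination".

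**The concern.** Follow-up from Day 43 to Month 13 serves mainly to find delayed serious and immune-mediated events. Appendix 8 of the protocol records that the Month 13 endpoint was moved from secondary to primary after regulatory feedback. For that endpoint, Protocol 9.4.3.2 asks how many participants in each group had an SAE or pIMD and how many of those events were judged related.

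If SAP 9.1.2 is followed exactly, the first count is produced and the second is not. A reader of the final tables could compare all-cause SAEs and pIMDs between the six vaccine groups and placebo, but could not see a count of related ones. Someone would have to build that count by hand from listings. The omission is not declared in SAP 11, so it would probably go unnoticed until the report is written.

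**Working it through.** The plan gives no figure to reproduce here. The check is a comparison of texts and one calculation of follow-up coverage.

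**1. Is relationship available?** Yes. Protocol 8.3.3 requires a causality assessment with every initial SAE or pIMD report, and Protocol 10.3.9.2 defines the question asked. The gap is in the planned tables, not in the data.

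**2. Which tables would show it?**

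| Event | SAE or pIMD table (SAP 9.1.2, second block) | Relationship table (first block) |
|---|---|---|
| Related SAE or pIMD, onset within 21 days of a dose | Counted, relationship not shown | Counted as an unsolicited AE, not identified as an SAE or pIMD |
| Related SAE or pIMD, later onset | Counted, relationship not shown | Not counted |

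The first row holds because unsolicited AEs include serious ones (Protocol 10.3.4, SAP 3.1), and every AE that is not solicited is recorded as unsolicited (Protocol 10.3.1.1). Of the two long-term categories, SAEs and pIMDs, neither has a relationship table at either cut-off.

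**3. How much of the Month 13 follow-up lies outside the relationship tables?** Inputs: optimal interval from Visit 1 to the Month 13 contact 385 days, allowed range 375 to 395 (Protocol Table 2, SAP Table 3); two windows of 21 days.

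- Days covered: 2 × 21 = 42.
- Days not covered: 385 − 42 = 343, and 343/385 = 89.1%.
- At 375 days: 375 − 42 = 333, or 88.8%. At 395 days: 395 − 42 = 353, or 89.4%.
- With the 403-day participation stated in Protocol 4.1: 403 − 42 = 361, or 89.6%.

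**4. How much of the Day 43 period?** Count the day of vaccination as the first of the 21 days, as Protocol 10.3.8 does for diary recording. Doses on Days 1 and 22 then give windows of Days 1 to 21 and 22 to 42, which is 42 of 43 days. If the second dose falls on Day 25, the latest allowed, Days 22 to 24 are uncovered (3 days). At Day 43, then, the issue is almost entirely that serious and immune-mediated events are not identified within the related-AE tables. Few events would be missing from those tables.

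**The case against.** The strongest defence is that the SAP follows the protocol's own objectives table. Table 3 and SAP 3.2.1 both say occurrence only. The list of separate summaries in Protocol 9.4.3.2 names SAEs, pIMDs and related AEs side by side without crossing them, and that section describes an AE analysis limited to onset within 21 days of the latest dose. SAP 9.1.2 has the same structure. This stands in part: the protocol disagrees with itself, and a reader who infers that the SAP departs from a single clear protocol requirement goes too far. It does not remove the point. The 21-day limit cannot govern an endpoint in the same section that runs to Month 13, and relationship is stated there for both windows.

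A second objection is that nothing is lost. A reader might infer that late related events reach no table. That is not so: they are counted in the SAE and pIMD tables to end of study and appear in the listings. Only the related/not-related classification is absent from the tables.

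A third is that those who need causality will have it. A reader might infer from the restriction on listings at Day 43 that the sponsor and regulators could not learn relationship. The documents do not support this. Causality comes with each expedited report (Protocol 8.3.3), unexpected SAEs suspected to be attributable are unblinded before regulatory reporting (Protocol 6.3.5.2), attributable SAEs can trigger the holding rules (Protocol 8.2.2.3), and the iSRC receives listings of related events (SAP 10.1). These routes serve case-by-case safety oversight. They do not give counts by study group, and the two scheduled iSRC reviews cover about 140 participants for 7 days after each dose.

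Finally, the separate table of contents for the outputs, mentioned in SAP 10.1, was not available and might already contain such a table. The SAP text does not specify one.

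**Conclusion.** The point holds as a reporting gap. Two primary safety endpoints, as worded in Protocol 9.4.3.2, include relationship, and SAP 9.1.2 plans no table of SAEs or pIMDs by relationship for either. The gap matters mainly for Month 13, where about 343 of 385 days (89%) lie outside every relationship table. It is small for Day 43.

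The 89% should not be read as a share of information or events lost. The documents give no expected number of late related SAEs or pIMDs. If there are few, the Month 13 listings will identify each one.

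The conclusion assumes that both planned doses are given, that the listings show the investigator's relationship assessment (SAP 9.1.2 does not describe their content), and that no unseen output specification already fills the gap. It does not affect participant protection or the immunogenicity analysis.

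**What to change.** 1. In SAP 9.1.2, present the SAE and pIMD tables by SOC, PT and maximum relationship, or add related-SAE and related-pIMD rows, by study group and age group. Do this mainly for Day 1 to Month 13 and also for Day 1 to Day 43. Since Protocol 10.3.9.2 collects causality as yes or no, a related row would be enough.
2. Align Protocol Table 3 and SAP 3.2.1 with Protocol 9.4.3.2, so that the endpoint has one wording. If the sponsor means occurrence only, SAP 11 should instead declare and justify leaving relationship out.

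The cost is SAP wording and a few extra tables from causality data already collected. Correcting Table 3 can wait for the next protocol amendment, and the new tables do not depend on it. No new data or procedures are needed.
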